4.7 Sensitivity to Sound was  ☐ Mild ☐ Moderate ☐ Severe
4.8 Tiredness was  ☐ Mild ☐ Moderate ☐ Severe
4.9 Vomiting was  ☐ Mild ☐ Moderate ☐ Severe
4.10 Which one of the following symptoms other than pain was most bothersome to you? (Select one) [Only if at least 1 "Yes" to 4]  [Present those with "YES" response to #4]  Aura [if selected for #4]
Dizziness or vertigo [if selected for #4]
Mental Slowness or Fogginess [if selected for #4]
Nausea [if selected for #4]
Neck Pain [if selected for #4]
Sensitivity to Light [if selected for #4]
Sensitivity to Sound [if selected for #4]
Tiredness [if selected for #4]
Vomiting [if selected for #4]
Another symptom was most bothersome [if at least one symptom was selected for #4]

[figure not shown]

5	Were any of the following difficult? (check all that apply)  Bending Forward [if yes, present 5.1]
	Concentrating [if yes, present 5.2]
	Getting Ready for the Day (e.g., get showered and dressed) [if yes, present 5.3]
	Keeping Your Plans for the Day [if yes, present 5.4]
	Moving Your Body [if yes, present 5.5]
	Moving Your Head [if yes, present 5.6]
	Remembering the correct words for things [if yes, present 5.7]
	Speaking Clearly [if yes, present 5.8]
	Strenuous Physical Activity [if yes, present 5.9]
	Thinking Clearly [if yes, present 5.10]
	Walking [if yes, present 5.11]
	None of the above [unavailable to select if any other option is selected; if selected END]
[If	YES to corresponding response to #6 present 1 item per screen]

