#### 8.1.2 MiCOAS Daily Assessment (MiCOAS DA)

The MiCOAS-DA is a *de novo* assessment intended to be completed by participants on a daily (calendar day) basis. The content of the items is spread across 2 general item and 3 individual measures:

- Symptoms (10 items)
- Subjective Mental Acuity (5 items; includes 1 symptom item)
- Physical Function (7 items)

The MiCOAS-DA also includes two general items asking about the participants day with respect to their experience. These two items ("Did you have a migraine day?" and "Did you have a good day?") of the MiCOAS DA use a Yes/No response scale. Nine of the symptom items use a 4-category ordinal response scale, with verbal labels (0 = Did not have to 3 = Severe verbal labels). One symptom item asks which symptom experienced was most bothersome. The remaining 11 non-symptom items use 5-category ordinal response scales, with verbal labels varying depending on item content. Most symptom items use a severity response scale (0 = Did not have to 4 = Severe verbal labels) while the non-symptom mental acuity and function items use a difficulty response scale (verbal labels ranging from 0= Not at all difficult to 4 = Unable to do).

Additionally, MMDs is a common outcome in preventive migraine trials, several other symptom and symptom-related items not included in the MiCOAS-DA based on relevance/importance to patients, such as duration of

head pain, medication use, and unilaterality of pain, are also included in the DA to allow for the identification of a migraine day and, when summarized, the calculation of MMDs.

A copy of the MiCOAS DA items can be found in Appendix C.

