### 14 APPENDIX C - MICOAS DAILY ASSESSMENT (MICOAS DA)

NOTE: For ease of review, items seen at every administration are presented in **bold**. Items seen based on participant responses/conditional logic are presented in *italics*.

ln '	the past 24 hours
1.	Did you have a good day?  ☐ Yes ☐ No
2.	Did you have a migraine day?  ☐ Yes ☐ No
3.	Did you have a headache or head pain?  □ Did not have □ Mild □ Moderate □ Severe
	3.1 How long did the headache last? [if #3 >= Mild] 30 minutes or less More than 30 minutes but 2 hours or less More than 2 hours but less than 4 hours 4 hours or more
	3.2 Did your head pain get worse with activity [if #3 >= Mild]  ☐ Yes ☐ No
	3.3 Did you have throbbing/pounding head pain? [if #3 >= Mild]  ☐ Yes ☐ No
	3.4 Did you have pain only or worse on one side of your head? [if #3 >= Mild]  ☐ Yes ☐ No
	3.5 Did you take any medication to alleviate your head pain? [if #3 >= Mild]  ☐ Yes ☐ No
	3.6 Did you seek care from a health care provider today because of your headache or head pain? [if #3 >= Mild]  ☐ Yes ☐ No
4	Did you experience any of the following? (check all that apply)  Aura (e.g., visual spots or flashes of light, skin tingling or numbness) [if yes, present 4.1]  Dizziness or vertigo [if yes, present 4.2]  Mental Slowness or Fogginess [if yes, present 4.3]  Nausea [if yes, present 4.4]  Neck Pain [if yes, present 4.5]  Sensitivity to Light [if yes, present 4.6]  Sensitivity to Sound [if yes, present 4.7]  Tired [if yes, present 4.8]  Vomiting [if yes, present 4.9]  None of the above [unavailable to select if any other response is selected; if selected go to #5]

[If YES to corresponding response to #4 present 1 item per screen]

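### Diary item 4.10 excludes pain in its stem but offers neck pain as an answer, so respondents most bothered by neck pain can answer differently depending on how they read the stem

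*Protocol*

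**What the plan says.** Protocol Appendix C handles head pain first and by itself: item 3 asks "Did you have a headache or head pain", with follow-ups 3.1 to 3.6 on that pain. Item 4 is a tick list of nine other symptoms, among them "Neck Pain [if yes, present 4.5". Each ticked symptom is rated for severity at 4.1 to 4.9, neck pain at 4.5.

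Item 4.10 then asks "Which one of the following symptoms other than pain was most bothersome to you". It appears after any single tick at item 4 and shows only the ticked symptoms, including "Neck Pain [if selected for #4", together with a fallback: "Another symptom was most bothersome [if at least one symptom was selected for #4". Head pain is not among the options.

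Section 8.1.2 describes the item without any pain exclusion: "One symptom item asks which symptom experienced was most bothersome".

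**The concern.** The stem and the answer list contradict each other. Neck pain is a pain, so the stem rules it out, but the screen offers it. A literal reader passes over neck pain even when it was the worst symptom. A reader who takes the stem to mean head pain selects it. Nothing else in the diary records which reading was used.

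Section 8.1.2 places the item among the symptom items of the daily assessment. Section 4.2 makes describing item properties a goal for that instrument, and Section 9.5 plans item-level descriptive statistics. The distribution of the most bothersome symptom is therefore something the study will report, and part of it would depend on how respondents read one word.

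**Working it through.** No sample size, power or error rate is involved, and the plan gives no figure to reproduce. The check is to set the items side by side and follow the branching.

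**Is it a text-extraction fault?** No. Neck pain appears in three separate places in Appendix C: as a tick option at item 4, as severity item 4.5, and as an option at 4.10.

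**Is the bare word pain used consistently for head pain?** No. Item 3 and its follow-ups name the headache, the head pain, or pain on one side of the head. The 4.10 stem drops the qualifier.

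**What does the respondent see at 4.10?**

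| Ticked at item 4 | Named options shown | Named options that fit the literal stem |
|---|---|---|
| Neck pain only | 1 | 0 |
| Neck pain and k others | k + 1 | k |
| k symptoms, not neck pain | k | k |

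- *Neck pain only.* A literal reader has only the fallback left. A fallback answer on such a day is then ambiguous: an unlisted symptom may really have been worse, or the stem may have steered the respondent away from neck pain.
- *Neck pain and others, neck pain worst.* A literal reader names one of the k others or the fallback; another respondent names neck pain.
- *Neck pain not ticked.* No conflict.

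**Which way would the distribution move?** If only head pain was to be excluded, literal readers can move answers away from neck pain and no one is moved towards it, so neck pain can only be under-counted by this route. If all pain was to be excluded, every neck-pain answer is off-question and takes the place of the non-pain answer that was wanted. Under either intent, the stem or the list is wrong.

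**How far does it reach?** The severity items are answered separately from 4.10. The migraine-day definition in Section 8.1.10 rests on head pain and its features, nausea or vomiting, photophobia, phonophobia and acute medication; it uses neither 4.10 nor neck pain. The primary objective (Section 4.1) concerns the recall measures.

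**Can a size be given?** Only an outer limit on diary days. With the planned completers and full compliance, this is 150 × 56 + 350 × 28 + 500 × 28 = 8,400 + 9,800 + 14,000 = 32,200. The number affected is a fraction of these. It depends on how often neck pain is ticked, how often it is then the worst symptom, and how many respondents read the stem literally. The protocol gives none of the three.

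**The case against.** The best defence is context. By the time respondents reach 4.10 they have answered a block on head pain, ticked neck pain and rated it, and they are then shown a list that names it. Most may take the stem to mean head pain, and the clearer that is, the fewer will be misled. This stands as a reason to expect a modest effect. It does not remove the contradiction, and the protocol does not say whether this stem was tested, although Section 3.2 mentions cognitive debriefing.

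It is also fair that no respondent is blocked, since the fallback is always offered, and that items 4 and 4.5 still record the presence and severity of neck pain. Days with neck pain could be examined by comparing 4.10 with 4.1 to 4.9. That is a partial check only, because severity is not the same as bother.

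Finally, the items are drafts and the study exists to refine them. That supports a low ranking, but it is no reason to field a known contradiction that can be settled beforehand.

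**Conclusion.** The point holds as a minor one. Stem and list contradict each other, and following the plan as written can make the same experience yield different answers. If the intended exclusion is head pain, neck pain may be under-counted in one nominal item of the secondary-objective instrument.

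A reader might go further and infer that neck-pain days will be answered inconsistently, or that neck pain will be under-counted. The protocol holds no response data, so only *can* and *may* are supported. A reader might also try to size the effect. Assuming neck pain is ticked on 30–60% of symptomatic days and is the worst symptom on 10–20% of those gives 0.30 × 0.10 = 3% to 0.60 × 0.20 = 12%. Nothing in the protocol supports either input, and the product leaves out the share who read the stem literally. It would describe days exposed to the ambiguity, not days answered wrongly, and should not be used as an estimate.

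That head pain alone was meant is an inference from the separate item 3 and from the absence of head pain from the list. The protocol does not state it.

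**What to change.** The instrument's developers should state which exclusion they intend, and stem and list should be aligned before fielding.

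- **Only head pain excluded** (the likelier intent): reword the stem to 'other than headache or head pain', matching item 3, and leave the option list unchanged.
- **All pain excluded**: remove Neck Pain from the 4.10 list, and do not show 4.10 when neck pain is the only symptom ticked.

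In either case, add the chosen exclusion to the description in Section 8.1.2.

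The cost is a short text edit in the electronic build, plus a change to the display rule under the second option. No planned analysis changes. The small downside is altering the wording of an item that may already have been through cognitive debriefing, so the developers should confirm that the new stem is acceptable.

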	5.1 Bending forward was
	$\Box$ A little difficult $\Box$ Somewhat difficult $\Box$ Very difficult $\Box$ Unable to do
	27 thete diffrence 2 sometimae diffrence 2 very diffrence 2 smalle to do
	5.2 Concentrating was
	$\square$ A little difficult $\square$ Somewhat difficult $\square$ Very difficult $\square$ Unable to do
	5.3 Getting ready for the day (e.g., get showered and dressed) was
	$\square$ A little difficult $\square$ Somewhat difficult $\square$ Very difficult $\square$ Unable to do
	5.4 Keeping your plans for the day was
	☐ A little difficult ☐ Somewhat difficult ☐ Very difficult ☐ Unable to do
	□ A tittle dijjicult □ somewnat dijjicult □ very dijjicult □ onable to do
	5.5 Moving your body was
	$\square$ A little difficult $\square$ Somewhat difficult $\square$ Very difficult $\square$ Unable to do
	5.6 Moving your head was
	$\square$ A little difficult $\square$ Somewhat difficult $\square$ Very difficult $\square$ Unable to do
	27 thete diffrence 2 semential diffrence 2 for y diffrence 2 smaller to do
	5.7 Remembering the correct words for things was
	$\square$ A little difficult $\square$ Somewhat difficult $\square$ Very difficult $\square$ Unable to do
	5.8 Speaking clearly was
	$\square$ A little difficult $\square$ Somewhat difficult $\square$ Very difficult $\square$ Unable to do
	5.9 Strenuous physical activity was
	$\square$ A little difficult $\square$ Somewhat difficult $\square$ Very difficult $\square$ Unable to do
	5.10 Thinking clearly was
	$\square$ A little difficult $\square$ Somewhat difficult $\square$ Very difficult $\square$ Unable to do
	5.11 Walking was
	$\Box$ A little difficult $\Box$ Somewhat difficult $\Box$ Very difficult $\Box$ Unable to do
	BA fittle difficult B somewhat difficult B very difficult B oliable to do

### 15 APPENDIX D - MICOAS RECALL-BASED MEASURES

Th	e following questions are about your experiences over the past 7/14 days.
In 	the past [7 days   14 days]
1.	On how many days did you have migraine symptoms?
	Drop down/check box choice of 0-7 or 0-14
2.	How often did you feel good?
	□ Never □ Rarely □ Sometimes □ Often □ Always
3.	How often were you able to enjoy all or part of a day?
	□ Never □ Rarely □ Sometimes □ Often □ Always
4.	How often did you want to spend time alone in a comfortable environment?
	□ Never □ Rarely □ Sometimes □ Often □ Always
5.	Was it difficult for you to do your usual day-to-day activities?
	□ Never □ Rarely □ Sometimes □ Often □ Always
6.	Was it difficult for you to take care of people or pets that you usually take care of?
	$\square$ Does not apply to me $\square$ Never $\square$ Rarely $\square$ Sometimes $\square$ Often $\square$ Always
7.	Was it difficult for you to manage your usual tasks and responsibilities at school or at work?
	$\square$ Does not apply to me $\square$ Never $\square$ Rarely $\square$ Sometimes $\square$ Often $\square$ Always
8.	How often were you too tired to do your regular daily activities?
	□ Never □ Rarely □ Sometimes □ Often □ Always
9.	How often did you have to miss your regular daily activities? Include times that you stopped early or started late.
	□ Never □ Rarely □ Sometimes □ Often □ Always
10.	. Was it difficult for you to do usual activities that require physical exertion, like going up stairs?

19. Was it difficult for you to enjoy social activity with other people?
$\square$ Not difficult at all $\square$ A little difficult $\square$ Somewhat difficult $\square$ Very difficult $\square$ Unable to do
20. Was it difficult for you to take part in activities you do for fun?
□ Never □ Rarely □ Sometimes □ Often □ Always
21. How often did you feel you did not have control over your life?
□ Never □ Rarely □ Sometimes □ Often □ Always
22. How often did you feel worried about having a migraine attack?
□ Never □ Rarely □ Sometimes □ Often □ Always
23. How often were you concerned that your migraine attacks would affect other people's lives?
□ Never □ Rarely □ Sometimes □ Often □ Always
24. How often did you feel sad or depressed?
□ Never □ Rarely □ Sometimes □ Often □ Always
25. How often did you feel frustrated?
□ Never □ Rarely □ Sometimes □ Often □ Always
26. How often did you feel irritable?
□ Never □ Rarely □ Sometimes □ Often □ Always
27. Was it difficult for you to concentrate?
□ Never □ Rarely □ Sometimes □ Often □ Always
28. Was it difficult for you to speak clearly?
□ Never □ Rarely □ Sometimes □ Often □ Always

29. Was it difficult for you to remember the right word for something?
$\square$ Never $\square$ Rarely $\square$ Sometimes $\square$ Often $\square$ Always
30. Was it difficult for you to have a conversation?
$\Box$ Not difficult at all $\Box$ A little difficult $\Box$ Somewhat difficult $\Box$ Very difficult $\Box$ Unable to do
31. Was it difficult for you to understand what was said to you?
$\Box$ Not difficult at all $\Box$ A little difficult $\Box$ Somewhat difficult $\Box$ Very difficult $\Box$ Unable to do
32. Was it difficult for you to understand what you were reading?
$\Box$ Not difficult at all $\Box$ A little difficult $\Box$ Somewhat difficult $\Box$ Very difficult $\Box$ Unable to do
33. Was it difficult for you to make day-to-day decisions?
$\Box$ Not difficult at all $\Box$ A little difficult $\Box$ Somewhat difficult $\Box$ Very difficult $\Box$ Unable to do
34. Was it difficult for you to carry out tasks that required many steps?
$\Box$ Not difficult at all $\Box$ A little difficult $\Box$ Somewhat difficult $\Box$ Very difficult $\Box$ Unable to do
35. Was it difficult for you to remember things that were important to you?
☐ Never ☐ Rarely ☐ Sometimes ☐ Often ☐ Always
36. Was it difficult for you to do tasks that required you to concentrate?
□ Never □ Rarely □ Sometimes □ Often □ Always

# 16 APPENDIX E - THE MIGRAINE FUNCTIONAL IMPACT QUESTIONNAIRE (MFIQ) VERSION 2.0

The following questions are about your ability to function in the past 7 days. We would like to understand how a migraine affects your day-to-day activities. Symptoms of migraine can include headache pain, nausea, vomiting, or sensitivity to light or noise. We want you to think about the symptoms that you experience and how they impact your day-to-day activities. Please answer all questions by selecting the one option that best describes your experience.

1.	In the past 7	days, how ofte	n did a migrain	e limit your ab	pility to move your head?
	□ Never	□ Rarely	

Sometimes

	□ Often	□ Always
2.		days, how ofte walking, bendi		e limit your ab	oility to move your body? (For example
	□ Never	□ Rarely	Sometimes	□ Often	□ Always
3.	In the past 7 effort?	days, how ofte	n did a migrain	e limit your u	sual activities that required physical
	□ Does not ap	ply; do not usu	ıally do activitie	es that require	e physical effort
	□ Never	□ Rarely	

Sometimes

	□ Often	□ Always
4.	In the past 7 because of yo	•	n did you feel t	hat you need	ed to rest or lie down during the day
	□ Never	□ Rarely	□ Sometimes	□ Often	□ Always
5.	In the past 7	days, how ofte	n did you feel t	oo tired to do	things because of your migraine?
	□ Never	□ Rarely	Sometimes	□ Often	□ Always
6.					ady for the day?  Uery difficult = Extremely difficult
7.		• '	n did you have ushing hair, sho	-	pleting specific personal grooming g make-up)
<	□ Never `	□ Rarely	□ Sometimes		□ Always
0	In the past 7	days how ofto	n did a migrain	a affect your	daily routing or schodulo?
ο.	-	•	_	-	daily routine or schedule?
	

Never

	Rarely	

Sometimes

	Often	□ Always

9.	In the past 7 days, how often did you have to change your plans because of a migraine?
	□ Never □ Rarely □ Sometimes □ Often □ Always
10.	In the past 7 days, how difficult was it to do your usual chores at home ? (For example, tidying up, cleaning, preparing a meal, doing minor repairs)
	□ Not difficult □ A little difficult □ Moderately difficult □ Very difficult □ Extremely difficult
11.	In the past 7 days, how much did a migraine limit your ability to do your usual chores outside the <pre>home? (For example, shopping or running errands)</pre> <pre>□ Not at all □ Slightly □ Moderately □ Very much □ Extremely</pre>
12.	In the past 7 days, how much did a migraine affect your ability to do your usual work or study-related activities?
	
 
Does not apply; I have not worked or studied at all during the past week for reasons unrelated to the disorder. *work includes paid or unpaid work.
 

	□ Not at all □ Slightly □ Moderately □ Very much □ Extremely
13.	In the past 7 days, how much did a migraine affect your ability to take care of your family? Does not apply I do not live with family.  Not at all  Slightly  Moderately  Very much  Extremely
14.	In the past 7 days, how difficult was it for you to do activities that required you to concentrate ?  Not difficult   Kery difficult   Extremely difficult
15.	In the past 7 days how difficult was it to do activities in the presence of loud noises, strong smells or bright lights?
	
 
Does not apply; I do not need to do activities in the presence of loud noises, strong smells, or bright lights.
 

	□ Not difficult □ A little difficult □ Moderately difficult □ Very difficult □ Extremely difficult
16.	In the past 7 days, overall, how much did a migraine affect your usual activities? Not at all  Slightly  Moderately  Very much  Extremely
17.	In the past 7 days, how much did a migraine affect your usual social interactions ? (For example, with family, friends, or coworkers)
	□ Not at all □ Slightly □ Moderately □ Very much □ Extremely
18.	In the past 7 days, how often did you avoid being around other people because of a migraine?  Never

19	D. In the past 7 days, how much did you have to limit your social activities because of a migraine?  — Not at all — Slightly — Moderately — Very much — Extremely
20	In the past 7 days, how often did a migraine interfere with your relationship with your partner of spouse?
	□ Does not apply; do not have a partner or spouse
	□ Never □ Rarely □ Sometimes □ Often □ Always
21	. In the past 7 days, how often did a migraine limit your usual leisure activities?
	□ Never □ Rarely □ Sometimes □ Often □ Always
22	
 
In the past 7 days, how frustrated did you feel about being unable to do what you needed to do because of a migraine?
 
Not at all Slightly Moderately Very much Extremely
 

	a Not at all a Stightly a moderately a very much a Extremely
23	3. In the past 7 days, how often did you worry about your migraines?
	□ Never □ Rarely □ Sometimes □ Often □ Always
24	I. In the past 7 days, how often did you feel like a burden on others because of a migraine?
	□ Never □ Rarely □ Sometimes □ Often □ Always
25	i. In the past 7 days, how often did you feel you lacked control of your life because of a migraine?
	□ Never □ Rarely □ Sometimes □ Often □ Always
26	o. In the past 7 days, how disappointed did you feel about having a migraine?
	□ Not at all □ Slightly □ Moderately □ Very much □ Extremely

# 17 APPENDIX F - MIGRAINE-SPECIFIC QUALITY OF LIFE QUESTIONNAIRE (MSQ) (VERSION 2.1)

PA	TIENT INSTRUCTIONS:
	ease fill out this questionnaire. It will help us understand the effects of migraine headache on your ily activities.
	e questionnaire has been designed so that it can be completed quickly and easily. Please check only e answer for each question. You should answer every question.
Th	ank you for your time.
	nile answering the following questions, please think about all migraine attacks you may have had in the ast 4 weeks.
1.	In the past 4 weeks, how often have migraines interfered with how well you dealt with family, friends and others who are close to you? (Select only one response.)  None of the time A little bit of the time A good bit of the time Most of the time All of the time All of the time
2.	In the past 4 weeks , how often have migraines interfered with your leisure time activities, such as reading or exercising? (Select only one response.)  None of the time  A little bit of the time  Some of the time  A good bit of the time  Most of the time  All of the time
3.	In the past 4 weeks , how often have you had difficulty in performing work or daily activities because of migraine symptoms? (Select only one response.) Difficulty in performing work or daily activities because of migraine symptoms? (Select only one response.) Difficulty in performing work or daily activities because of migraine symptoms? (Select only one response.) Difficulty in performing work or daily activities because of migraine symptoms? (Select only one response.) Difficulty in performing work or daily activities because of migraine symptoms? (Select only one response.) Difficulty in performing work or daily activities because of migraine symptoms? (Select only one response.) Difficulty in performing work or daily activities because of migraine symptoms? (Select only one response.) Difficulty in performing work or daily activities because of migraine symptoms? (Select only one response.) Difficulty in performing work or daily activities because of migraine symptoms? (Select only one response.) Difficulty in performing work or daily activities because of migraine symptoms? (Select only one response.) Difficulty in performing work or daily activities because of migraine symptoms? (Select only one response.) Difficulty in performing work or daily activities because of migraine symptoms? (Select only

☐ All of the time

4.	In the past 4 weeks , how often did migraines keep you from getting as much done at work or at home?  (Select only one response.)  None of the time  A little bit of the time  A good bit of the time  Most of the time  All of the time
5.	In the past 4 weeks, how often did migraines limit your ability to concentrate on work or daily activities?  (Select only one response.)  None of the time  A little bit of the time  A good bit of the time  Most of the time  All of the time
6.	In the past 4 weeks, how often have migraines left you too tired to do work or daily activities? (Select only one response.)  None of the time  A little bit of the time  A good bit of the time  Most of the time  All of the time
7.	In the past 4 weeks , how often have migraines limited the number of days you have felt energetic? (Select only one response.)  None of the time  A little bit of the time  A good bit of the time  Most of the time  All of the time
8.	In the past 4 weeks, how often have you had to cancel work or daily activities because you had a migraine? (Select only one response.)  None of the time A little bit of the time Some of the time A good bit of the time Most of the time All of the time

9.		ne past 4 weeks , how often did you need help in handling routine tasks such as every day household res, doing necessary business, shopping, or caring for others, when you had a migraine? (Select only
		response.)
		None of the time
	_	A little bit of the time Some of the time
		A good bit of the time
		Most of the time
		All of the time
10.		ne past 4 weeks , how often did you have to stop work or daily activities to deal with migraine
	_	nptoms? (Select only one response.)  None of the time
		A little bit of the time
		Some of the time
		A good bit of the time
		Most of the time
		All of the time
11.		ne past 4 weeks , how often were you not able to go to social activities such as parties, dinner with
	frier	nds, because you had a migraine? (Select only one response.)
		None of the time
	_	A little bit of the time
		Some of the time
		A good bit of the time
		Most of the time All of the time
	_	Att of the time
12.	. In th	ne past 4 weeks, how often have you felt fed up or frustrated because of your migraines? (Select only
		response.)
		None of the time
		A little bit of the time
		Some of the time
		A good bit of the time
		Most of the time
		All of the time
12	In th	ne past 4 weeks, how often have you felt like you were a burden on others because of your migraines?
13.		lect only one response.)
		None of the time
		A little bit of the time
		Some of the time
		A good bit of the time
		Most of the time
		All of the time

14. In (So	the past 4 weeks , how often elect only one response.)  None of the time  A little bit of the time  Some of the time  A good bit of the time  Most of the time  All of the time	have you been afraid of let	tting others down becaus	ee of your migraines?
			S	On
		ACHO.		

